#### 9.4 Objectives/Specific Aims/Research Questions:

Describe the purpose and objective(s) of the study, specific aims, and/or research questions/hypotheses

**Objective:** To evaluate the efficacy of acute riluzole treatment (100-200mg/day) in 158 active duty and returning OIF, OEF, and OND veterans, aged 18 to 65 with a diagnosis of PTSD, with or without mTBI, who are sub-optimally responsive to their current medication treatment (8 weeks).

**Hypothesis 1:** *Subjects with PTSD, with or without mTBI, who are only partially responsive to initial therapy (e.g., CAPS score greater than or = 40 at the completion of an adequate trial of medication therapy) who are subsequently randomized to augmentation therapy with riluzole will have a superior response rate compared to subjects randomized to placebo.*

**Hypothesis 2:** *PTSD patients randomized to augmentation with riluzole therapy will have significant improvement in depression, anxiety and global functioning compared to those who receive placebo in addition to their pre-study PTSD medication.*

**Hypothesis 3:** *The N-acetyl aspartate to creatine ratio (NAA/Cr) in the hippocampus and anterior cingulate, measured using magnetic resonance spectroscopy (H MRS), will increase after 8-week treatment with riluzole.*

In addition to indicating simple change in severity, the change in CAPS total score will be the primary outcome variable at the end of Phase II (Visit 10). We believe this study is powered to detect a 9 point or greater difference in CAPS total score from baseline between riluzole and placebo augmentation (after Phase I) to the last measured value of Phase II.

The following scales are proposed for primary and secondary outcome measures:

- i. Primary Outcomes Assessment:** Clinician-Administered PTSD Scale (CAPS), Clinical Global Impression of Severity (CGI-Severity), Clinical Global Impression of Improvement (CGI-Improvement).
- ii. Secondary Outcomes Assessment:** Montgomery-Asberg Depression Rating Scale (MADRS), Hamilton Anxiety Rating Scale (HAM-A), Sheehan Disability Scale (SDS), PTSD Checklist (PLC-C), UKU Side Effect Rating Scale, Self-rating version.
- iii. Additional secondary outcome measure:** Changes in NAA levels in the hippocampus and anterior cingulate cortex following riluzole or placebo administration measured using H MRS.

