**Abbreviations:** Sc = Screening Visit; Sta = Stabilization Visit; CAPS = Clinician-Administered PTSD scale; CD-RISC = Connor-Davidson Resilience Scale; CGI = clinical global impression scale; CTQ = Childhood Trauma Questionnaire; DES = Dissociative Experience Scale; F/U = Follow-up visit; HAM-A = Hamilton Anxiety Rating Scale; HCG = blood pregnancy test; Hollingshead = Hollingshead 4 Factors of Social Status Scale; LSAS = Liebowitz Social Anxiety Scale; MADRS = Montgomery Depression Rating Scale;; PLC-C = PTSD Checklist; UKU-SERS-Pat = UKU Side Effect Rating Scale, Self rating version; PDI = Peri Traumatic Distress Inventory; PSQI = Pittsburgh Sleep Quality Index; SCID-IV-TR = Structure Clinical Interview for DSM-IV; SCR = screen; SCL-90 = Symptom Checklist, 90 items; SDS = Sheehan Disability Scale; WHOQOL BREF = World Health Organization Quality of Life WO = washout phase.

aExit visit to be performed at Visit 9 or sooner if the patient is discontinued from the study.

WO = washout phase. May vary depending on drug but in general is 51/2 lives. If the subject is medication free, they may proceed to Study Period I.

bVisits during Study Period II may happen within 2 days of the scheduled visit. SCO = Standard of Care activity - Affirmative notation; Default notation is left blank indicating an activity that is research-related.

The 10-week clinical study will be conducted in two phases, a minimum of 2-weeks and maximum of 4-weeks screening and stabilization phase (Phase I) and an 8-week double-blind placebo controlled treatment (Phase II).

In Phase I, indicated as the "Screening Period" in **Figure 1 Riluzole Augmentation for PTSD**, patients who are suboptimal responders (see inclusion/exclusion criteria) to other psychotropic drugs will continue these at stable dosage for at least 2 weeks prior to study randomization (dose stabilization). Use of antidepressant and sedative/hypnotic drugs at stable dose is permitted. Subjects will be contacted by phone after 1 week to assure that no medication changes were made and to schedule the first Phase II visit.

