Phase II, indicated as the "Acute Double-Blind Period", in **Figure 1 Riluzole Augmentation for PTSD**, begins after the completion of the stabilization phase, where subjects will be randomized at a ratio of 1:1 to receive an 8-week double-blind treatment of either riluzole or placebo. Riluzole or placebo will be administered in two divided doses (two tablets twice a day). During the clinical trial, all blinded study medication will be manufactured to identical appearance. All members of the research team and treatment staff will be blinded. Subjects will be assessed weekly from Visit 1 through Visit 9 (see Schedule of Events, **Section 5.5.8 Study Time Line**). Riluzole therapy will be initiated at a dose of 50mg twice daily, as will matching placebo for those subjects randomized to placebo. Riluzole may be increased to 200 mg/day thereafter if the subject's weekly case history (subject self-reported symptomatology and CAPS score and/or additional psychological clinical battery diagnostics) indicate that the increased dose may have therapeutic benefit. The maximal allowable dose of riluzole permitted is 200 mg/day. The minimal allowable dose of riluzole permitted is 100 mg/day. Those subjects unable to tolerate the lowest allowable dose will be discontinued from the study. Eligible subjects who consented to participate in the baseline  $^1\text{H}$  MRS portion of the study will undergo a post-treatment scan between visits 8 and 9.

The time commitment for the weekly scheduled visit is estimated to be 2-4 hours. The time commitment for the post-treatment  $^1\text{H}$  MRS scan is estimated to be 60 to 90 minutes.

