### Acute Trial Assessments

As shown in **Section 5.5.8 Study Time Line**, subjects participating in this study will be rated weekly during the double-blind phase for severity of PTSD using the same scales as were obtained at Visit 2. Week 8 or Visit 9 ratings will be used to determine whether patients meet criteria for response. Side effects will be assessed using the UKU side effect rating scale, self-rating version (Lindstrom et al., 2001).

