An 8-week open-label study with riluzole in treatment-resistant DSM-IV bipolar depression (Protocol #03-M-00092) (Zarate et al., 2005). Eight subjects (57%) completed the 8-week trial. The reasons for discontinuation were adverse events (N =3; 2 asymptomatic increase in liver function tests, 1 renal calculi) and lack of improvement (N =3). Patients received riluzole at a mean daily dose of 171.4 + 42.6 mg (79% took a dose of 150 mg/day or more). The most common adverse events during the trial were fatigue (N = 4), decreased salivation (N = 4), reduced sleep (N = 4), nausea (N = 3), diarrhea (N = 3), weight loss (N = 3), decreased sex drive (N = 3), blurred vision (N = 3), and headache (N = 3). No serious adverse events were noted. Two subjects were discontinued from the study because of increased liver function tests (LFTs) that were more than three times the upper normal limit. These subjects were asymptomatic for hepatic dysfunction, and LFTs normalized shortly after discontinuing riluzole. One additional subject was discontinued because of renal calculi. Overall riluzole was well tolerated.

A 6-week open-label study with riluzole in treatment-resistant DSM-IV major (unipolar) depression (Protocol #02-M-0034) (Zarate et al., 2004). Patients received riluzole at a mean daily dose of 168.8 + 27.2 mg (84.2% took a dose of 150 mg/day or more) for a mean duration of 5.4 ± 3.7 weeks. Sixty-eight percent (N=13) of subjects completed the 6-week trial. The reasons for discontinuation were adverse events N=3 (1 increased liver function tests, 1 malaise, 1 nausea/vomiting), non-response N=2, and administrative N=1. The most common adverse events during the trial were headache (58%), gastrointestinal distress (nausea or vomiting) (43%), decreased salivation (47%), constipation (32%), and tension/inner unrest (26%); similar side effects have been observed with riluzole in ALS trials (Bensimon et al., 1994). No serious adverse events were noted. One subject was discontinued from the study because of an increase in liver function tests (LFTs) that was 3 times the upper normal limit. This subject was asymptomatic for hepatic dysfunction, and LFTs normalized shortly after discontinuing riluzole. There was no relationship between dose of riluzole and adverse events or changes in laboratory tests.

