A condition called interstitial lung disease has occurred in some patients who have taken riluzole. Participants will be advised of this risk and informed that should they develop a dry cough with shortness of breath or difficulty breathing, they will need to seek medical attention including a chest x-ray assessment and will need to discontinue taking riluzole immediately.

**Risks Associated with Magnetic Resonance Spectroscopy:** H MRS is not associated with any known deleterious biological effects in normal subjects. However, there are risks for subjects who have any metallic implants in their body or who have an artificial cardiac pacemaker. For this reason, they will be screened for the presence of any metallic prostheses or cardiac pacemaker both at the time of recruitment, and just prior to H MRS imaging. Subjects will be advised of two potential discomforts. The first is that the procedure requires remaining still while lying on their back for an extended period of time (up to 60 minutes). The second is the MRS machine is a tightly enclosed space, which may be of concern for those with claustrophobia.

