Continuous monitoring of the participant's health while taking the assigned medication is performed by the Medical Monitor in conjunction with the Principal and Associate Investigators during the scheduled weekly visits. Participants will have clinical biochemistry laboratory blood assays performed to monitor their liver state and function. Liver Function Test (LFTs) will be run first at the Screening Visit and then weekly while taking the assigned medication. In the period between screening and randomization, the participant will be instructed not to begin taking study medication until the Investigator confirms that LFTs are within normal limits. Specifically, their alanine transaminase (ALT), aspartate transaminase (AST), total/direct bilirubin, and alkaline phosphate, will be monitored on a weekly basis during Study Period II to ensure that participants do not have liver function tests elevated over 3x normal ranges. If elevated LFTs are encountered, the test will be repeated, and if levels remain elevated at or above 3x upper limit of normal, the participants on the higher dose will have their dose reduced to 100mg per

day and participants on the low dose will be removed from the study. If a participant's LFTs ever exceed 5x upper limit of normal, the study drug will be discontinued and the subject will be withdrawn from the study.

Elevated LFTs of only 2xs level are not clinically uncommon and are often associated with any number of unrelated medical conditions or complications. A mild elevation in LFTs is quite often temporary in nature, and quickly reversible. Initial studies in riluzole established the 3x level as diagnostic for liver enzyme impairment or disruption to ensure that unrelated medical conditions and complications do not compromise the study while still ensuring the highest safeguarding of the participant.

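### In the visible text, drug-related stopping is also study exit, with one exit-visit CAPS and no planned week-8 CAPS; the loss is plausibly more frequent on riluzole

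*Combined protocol and SAP*

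**What the plan says.** Three rules join stopping drug to leaving the study:

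- Section 9.5, Phase II, on intolerance: "Those subjects unable to tolerate the lowest allowable dose will be discontinued from the study".
- Section 14.2 a, repeat liver tests still at or above 3x the upper limit: "participants on the low dose will be removed from the study". Those on the higher dose are dose-reduced instead.
- Section 14.2 a, liver tests above 5x: "the study drug will be discontinued and the subject will be withdrawn from the study".

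Footnote a to the schedule in 9.5 says what happens next: "Exit visit to be performed at Visit 9 or sooner if the patient is discontinued from the study". The Visit 9 column includes CAPS and CGI. No outcome assessment after that visit is described. The possible period of observation and the up to 90 days of continued care in 14.2 are clinical care.

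The endpoint value is described in two ways. Section 9.4 takes the CAPS difference from baseline "to the last measured value of Phase II", and 11.3 uses the same last value for its responder definition. Acute Trial Assessments (10.2) says: "Week 8 or Visit 9 ratings will be used to determine whether patients meet criteria for response". Section 11.1 prompts for the handling of missing data, but the table beneath it gives none. Section 13.7 on withdrawal refers only to a legacy protocol that is not in the file.

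**The concern.** Someone who stops drug at week 3 contributes a week-3 CAPS, while someone who stays contributes a week-8 CAPS. If stopping were rare and equally frequent in both arms, this would matter little. But intolerance and liver-enzyme rises are known effects of riluzole, so the mix of early and late values is likely to differ by arm for reasons connected with treatment.

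At stake is the week-8 comparison of everyone randomised. A value that was never collected can only be replaced by an assumption at the analysis stage. Restricting the analysis to week-8 values compares those who tolerated the drug with those who tolerated placebo. Using the last value compares different lengths of follow-up. Neither is the randomised comparison at week 8.

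**Working it through.** **1. The plan's own figure.** Section 11.2: difference 9, SD 15, 50 per arm, two-sided alpha 0.05. Noncentrality = 9 / (15 x sqrt(1/50 + 1/50)) = 3.0 on 98 degrees of freedom. Exact power is 0.844, as stated.

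**2. Margin for loss.** The only allowance is for ineligibility before randomisation, 30-40% of 158 consented: 158 x 0.60 = 94.8 and 158 x 0.70 = 110.6. That gives about 95 to 111 randomised against the 100 in the calculation. Nothing is set aside for loss after randomisation.

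**3. CAPS available for an early stopper.** In the schedule, CAPS after baseline is at Visit 6 (week 5) and Visit 9 (week 8) only. Someone who stops before week 5 therefore has the exit CAPS alone, and none if that visit is missed.

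**4. Is more stopping on riluzole plausible?** Section 14.1 calls nausea, asthenia and liver-enzyme elevation dose-related, and reports nausea at 12-21% on riluzole against 12% on placebo. In the bipolar cohort, "Eight subjects (57%) completed the 8-week trial", so n = 14, with 3 adverse-event stops (2 for liver tests). In the unipolar cohort 13 of 19 completed, with 3 adverse-event stops (1 for liver tests). Pooled, 6/33 = 18% stopped for adverse events and 3/33 = 9% for liver tests. Neither cohort had a placebo arm, so the direction is supported but the size of the between-arm difference is not.

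**5. What the two readings of the endpoint would do.** The documents give no loss rate for this trial, so every rate below is an assumption.

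(a) Week-8 values only, stoppers missing, 9-point difference kept:

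| Riluzole / placebo loss | Analysed | Power |
|---|---|---|
| 10% / 5% | 45 vs 48 | 0.816 |
| 18% / 5% | 41 vs 48 | 0.797 |

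(b) All 100 followed to week 8. If riluzole stoppers end at the placebo mean, the all-randomised difference is 9 x (1 - stopping rate):

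| Riluzole stopping | Difference | Power, 50 per arm | Overstatement by a completer estimate of 9 |
|---|---|---|---|
| 5% | 8.55 | 0.806 | 0.45 |
| 10% | 8.10 | 0.762 | 0.90 |
| 18% | 7.38 | 0.683 | 1.62 |

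(c) Last measured value, as in 9.4 and 11.3. Assume linear change to -19 (riluzole) and -10 (placebo) at week 8, and exit at week w. Arm mean = week-8 change x [(1 - p) + p x w/8].

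For 10%/5% and w = 2: riluzole -19 x (0.90 + 0.10 x 0.25) = -17.575; placebo -10 x (0.95 + 0.05 x 0.25) = -9.625; difference 7.95.

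| Loss | Exit week 2 | Exit week 4 |
|---|---|---|
| 10% / 5% | 7.95 | 8.30 |
| 18% / 5% | 6.81 | 7.54 |

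With no drug effect (both arms -10), the same rule moves the estimate against riluzole by 0.25 points (10%/5%, week 4) to 0.975 points (18%/5%, week 2).

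**6. Direction.** If stoppers would have kept the full benefit, the target is 9 and every value in (c) is too low. If they lose it, the targets are 8.10 and 7.38, and the values in (c) fall on either side of them. A completer analysis errs upward in that second case. The direction depends on what happens after stopping, which is what the plan does not measure.

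**The case against.** The strongest reply is that early leavers are not without an outcome. The exit visit carries CAPS and CGI, and the primary analysis uses the last measured value, so a leaver who attends is in the analysis as written. That stands. A reader might infer that stopping drug ends all assessment or removes people from the primary analysis; the schedule footnote and section 9.4 do not support this. What is missing is the week-8 value after stopping. The dose-escalation text in 9.5 also mentions CAPS among weekly information. If CAPS were in fact taken weekly, there would be more values before exit, but still none at week 8.

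Other stronger readings also fail:

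- That a week-8 value could never exist. Section 13.7 defers to a document not in the file. Section 14.1 says that people with respiratory symptoms "will need to discontinue taking riluzole immediately", without saying whether study visits continue.
- That worsening, or a change in psychotherapy or psychiatric medication, automatically ends participation. Section 14.2 leaves this to discretion.
- That each arm would lose the shares that failed to complete the open-label studies (6/14 and 6/19). Those counts are all-cause: 5 of the 12 stopped for lack of improvement or non-response and 1 for administrative reasons. They come from other disorders, and applying riluzole rates to placebo would contradict a difference between arms. Even 18% may not transfer, since half of those stops were for liver tests and 14.2 a here provides for a retest and, on the higher dose, a reduction first.

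**Conclusion.** The point holds in limited form. Three drug-related stops are written as study exits, the participant then has an exit CAPS only, and no week-8 CAPS is planned in the visible text. Sections 9.4 and 11.3 (last value) and 10.2 (week 8 or Visit 9) disagree on which value counts. More frequent loss on riluzole is plausible, but its size is unknown.

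The effect on the estimate is likely to be modest: in the illustrations, roughly 0.5 to 2 points on a 9-point target, in either direction. This rests on assumed stopping rates, linear change, exit at week 2 or 4 and, for the completer comparison, full loss of benefit after stopping. It is worth correcting because the remedy is cheap and analysis cannot supply the missing values. Confidence is medium, given the legacy protocol that is not in the file.

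**What to change.** Leave every treatment-stopping and safety-removal rule as it stands. In schedule footnote a and the Phase II text of 9.5, and in 14.2 a, separate stopping study drug from leaving study assessments:

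1. Keep the exit assessment at the time of stopping.
2. Then invite participants who still consent, and whom the investigator has not removed for safety or distress, to the scheduled Visit 9 (week 8) CAPS and CGI, and to Visit 6 if it has not passed.
3. Record treatment received in between, and use these values in the all-randomised week-8 comparison. Reconcile 9.4, 10.2 and 11.3 on which value is the endpoint.
4. State in 14.1 whether study visits continue after a respiratory stop.

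Withdrawal should not be narrowed to loss of consent, because that would override the removals for risk and for distress during questioning in 14.2.

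Cost: protocol and consent wording, and at most two already scheduled visits per early stopper. Some will decline, and some week-8 values will reflect other treatment and must be flagged. Continued follow-up also does not protect power. If stoppers lose benefit, holding 0.844 would need about 55, 61 or 73 per arm at 5%, 10% or 18% riluzole stopping, from n = 2 x (1.960 + 1.011)^2 x 15^2 / d^2 with d = 8.55, 8.10 or 7.38 (normal approximation).

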## 10.2 Data Collection:

Describe all the data variables, information to be collected, the source of the data, how the data will be operationally measured, and approvals needed for use of information from DoD databases

### a. Method of Collection from Study Participants.

**Primary Outcomes Assessment** – All study assessment materials are in the public domain and will not be altered. Each measure includes a minimum of one citation attesting to the reliability and validity of

the questionnaire based on the consensus of researchers published in the field of behavioral science. In general, each measure has a minimum assessment level of 'adequate', with the majority assessed at a level of 'good' or higher.

Instruments selected are well established neuropsychological questionnaires with extensive clinical and research validation and are structured to ensure the highest levels of clarity and ease of administration. Participants will have no difficulty in reliably completing these instruments in a clinical setting. This instrument battery is currently in use in several WRNMMC-approved research projects conducted by the Investigator in both the inpatient ward and outpatient clinics at WRNMMC. Further, this instrument battery is in use by the INTRuST Clinical Consortium, which is a multi-site research collaboration on PTSD and TBI, which will allow de-identified data from this study to be compared across a nationally-representative dataset. Assessments not directly related to the primary outcome are being made to allow for comparability with these other ongoing trials in this population, and all questionnaires were selected and rigorously reviewed to ensure that content overlap was minimized in the interest of participant welfare. As such, no unnecessary measures are included, and all data collected will be analyzed and results reported and disseminated.

**1. Clinician-Administered PTSD Scale (CAPS):** The CAPS (Blake et al 1995; Blake et al., 1990) is a lengthy structured interview based on the DSM-IV that assesses the presence and severity of PTSD and associated symptoms. Changes from baseline to endpoint in the CAPS total score will serve as the primary efficacy measure for the double blind phase. The CAPS is widely accepted as the Gold Standard for establishing PTSD diagnosis with excellent reliability and validity (Blake et al., 1990; 1995), (Weathers et al., 1999).

**2. Clinical Global Impression of Severity (CGI-Severity):** The CGI-Severity scale (Guy, 1976) will be administered to assess the clinician's global impression of the severity of the patient's PTSD at each visit over the course of treatment. It is a 7-point scale in which 1 = normal and 7 = extremely severe case of PTSD. The CGI is a core metric for psychiatric research and has demonstrated adequate psychometric properties (Berk et al., 2008).

**3. Clinical Global Impression of Improvement (CGI-Improvement):** The CGI-Improvement scale (Guy, 1976) will be administered to assess the clinician's global impression of the improvement of the patient's PTSD over the course of treatment. It is a 7-point scale in which 1 = very much improved, 4 = no change, and 7 = very much worse. A pre-entry score (e.g., for those subjects entering this protocol from other research studies) will be obtained during the screening phase. Those subjects who, at the completion of the previous research study receive scores of 1, 2, or 3 will be excluded from this study.

For this study, treatment response will be defined as those who are very much improved (score of 1), or much improved (score of 2), or improved (score of 3) on the Clinical Global Impressions, improvement item and have a  $\geq 9$  point decrease in CAPS score.

